	1 Day 3-hours	Day 1 7-9 hours	Day 2 optional	1 Day 1-hour	Day 1 7-9 hours	Day 2 optional
Procedures	Screening	Baseline		Compliance (Outpatient)	Outcome	
Informed Consent	X					
History and Physical (MMSE Visit 1 only)	X				X	
Review Inclusion/Exclusion Criteria	X	X				
Symptoms Review Questionnaire	X	X			X	
PANAS, RAND SF-36		X		X	X	
Cognitive Testing		X			X	
MRI		X			X	
Accelerometers	X				X	
Vital Signs	X	X		X	X	
Anthropometric measurements	X	X		X	X	
Urine Drug Screen	X					
Urine Pregnancy test	X	X			X	
Fasting Blood Draw	X	X		X	X	
Mixed Meal Tolerance Test		X			X	
Lumbar Puncture		X			X	
Dispense Diet Shakes (5-2 CR Group)		X		X		
Dietary Counseling-ALL Groups		X		X		
Meals / Snacks		X		X	X	
Follow-up Phone Call or Email				Weeks 1, 3, 5, 7	Follow-up	
Payment	\$50.00	\$350.00		\$150.00*	\$500.00	

Table 2: Laboratory

	Visit 1	Visit 2		Visit 3, 4, 5	Visit 6	
		Week 0		Weeks 2, 4, 6	Week 8	
	1 Day 3-hours	Day 1 7-9 hours	Day 2 optional	1 Day 1-hour	Day 1 7-9 hours	Day 2 optional
Laboratory	Screening	Baseline within 4 weeks of Screening Visit		Compliance (Outpatient)	Outcome	
Clinical Labs: CBC with differential, CMP, HbA1c, Phosphate, Magnesium, TSH, Liver Panel, Lipid Panel, Uric Acid, PT/INR, PTT, insulin, HIV, HBV, HCV	X					
Research Lab: Insulin	X					
Clinical Labs: CBC and PT/INR, PTT		X				
Research Labs: AD Biomarkers, Cytokines/Chemokines, Neurotrophic Factors, Exosomes, Oxidative Stress Biomarkers, gene expression and DNA methylation, WBC differential counts, β -hydroxybuterate		X				
CSF		X			X	
Research Labs: β -hydroxybuterate, gene expression and DNA methylation, WBC differential counts, plasma sample for AD Biomarkers, Cytokines/Chemokines, Neurotrophic Factors, Exosomes, Oxidative Stress Biomarkers				X		
Clinical Labs: CBC with differential, CMP, HbA1c, Phosphate, Magnesium, TSH, Liver Panel, Lipid Panel, Uric Acid, PT/INR, PTT, insulin					X	
Research Labs: AD Biomarkers, Cytokines/Chemokines, Neurotrophic Factors, Exosomes, Oxidative Stress Biomarkers, gene expression and DNA methylation, WBC differential counts, insulin, β -hydroxybuterate					X	

Amount of Blood	28 ml	168 ml	62 ml/visit	174 ml
-----------------	-------	--------	-------------	--------

4.d.2. Baseline visit

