This visit will occur within four weeks from the Screening Visit. Participants will arrive on the NIA-Clinical Research Unit after a 12-hour fast. The following procedures will be done: vital signs, anthropometric measurements (weight, waist circumference, sagittal diameter), and a blood draw for clinical labs (CBC, PT, PTT, and INR to ensure safety of the LP), urine pregnancy test (only in women who are able to become pregnant), and research labs including DNA collection (for APOE genotyping and gene expression studies). A 4-hour mixed meal tolerance test will be done. They will also have cognitive testing and will be asked to complete the Symptoms Review Questionnaire, PANAS, and RAND SF-36. A lumbar puncture (LP) will take place; up to a total of 15 mL of CSF will be collected. Participants will have a brain MRI. About 168 mL of blood will be taken during the visit. To facilitate scheduling or satisfy a given participant's request, we may split the various procedures of the Baseline Visit over two days within a week from each other.

4.d.3. 5-2 CR or control groups

At the end of the Baseline Visit, all participants will receive informational materials and one-on-one dietary counseling about "healthy living", consisting of providing and reviewing published material (by the CDC and USDA) on meal portion control, calories in common beverages, meal substitutions for controlling calorie intake, and other dietary considerations. Participants will then be randomized by study investigators into one of two groups to either 1) implement 8 weeks of 5-2 CR (cases); or 2) implement "healthy living" diet (controls).

Participants in the 5-2 group will receive all shakes (Boost®, CWI Medical) from the NIA-Clinical Research Unit.

4.d.4. Compliance visits

To assess and reinforce compliance with their respective diet, we will contact participants by phone or email (via the Secure Email & File Transfer Service: <https://secureemail.nih.gov/bds/Login.do>) at weeks 1, 3, 5, 7 and four days after the Outcome Visit. In addition, we will conduct 2, 4, and 6 week Compliance Visits. The same procedure described below will occur during each one of these.

These visits will take place during the second of the two consecutive restriction days for the 5-2 CR group or any day for the "healthy living" diet group after an 8 hour fast. A blood draw to measure β-hydroxybutyrate, vital signs and anthropometric

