measurements (weight, waist circumference, sagittal diameter) will be done. Participants will provide feedback regarding physical and psychological symptoms by completing a Symptoms Review Questionnaire and the RAND SF-36. Samples for β -hydroxybutyrate levels will be sent to Harbor Hospital Lab. In addition, a plasma sample will be sent to the NIA Core Lab for future studies. These visits will take about 1 hour.

In addition, blood will be collected for isolation of total RNA and genomic DNA for target pathways gene expression and methylation analyses, and PBMCs counts. 62 ml of blood will be collected during each one of these visits.

4.d.5. Outcome visit

The Outcome Visit will occur at the end of the 8-week period in the 5-2 CR or control group. This visit will take place during the first of the two consecutive constriction days for 5-2 CR participants or at a convenient time during the week for control participants. This visit will occur after a 12-hour fast, to ensure comparability of the mixed meal test with the Baseline Visit. The visit procedures will be similar to the Baseline Visit, including a lumbar puncture (LP) and a medical history and physical exam.

Participants will arrive on the NIA-Clinical Research Unit after a 12-hour fast. The following procedures will be done: vital signs, anthropometric measurements (weight, waist circumference, sagittal diameter), and a blood draw for clinical labs (CBC, PT, PTT, INR, CMP, lipid panel, uric acid, HgbA1c, insulin, β -hydroxybutyrate), urine pregnancy test (only in women who are able to become pregnant), and research labs including DNA collection (for gene expression studies). A 4-hour mixed meal tolerance test will be done. They will also have cognitive testing and will be asked to complete the Symptoms Review Questionnaire, PANAS, and RAND SF-36. A lumbar puncture (LP) will take place and up to a total of 15 mL of CSF will be collected. Participants will also have a brain MRI. About 174 mL of blood will be taken during each visit (including clinical and research labs). To facilitate scheduling or satisfy a given participant's request, we may split the various procedures of the Outcome Visit over two days within a week from each other.

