4-hour mixed meal tolerance test: After fasting for at least 12 hours, participants will be asked to drink 5 mL/Kg of the dietary supplement shake Ensure Plus®. Ensure Plus® is a mixed liquid meal; one bottle (480 mL) contains 95 g carbohydrate as dextrose, 26 g protein, and 25 g fat, providing 710 kilocalories. In addition, to inducing a change in glucose and insulin, the mixed meal tolerance test is ideal for testing changes in GLP-1, GIP, ghrelin, glucagon, pancreatic polypeptide, C-peptide, and other hormones. A blood draw will take place before subjects consuming the liquid meal. Plasma, serum and whole blood biomarkers will be measured from this blood draw. for biomarkers, hormones, and cytokines (approximately 35 mL). Then subjects will ingest the liquid meal, followed by blood draws every 20 minutes (5 mL per sample). Typically, participants will have an intravenous (IV) line placed in an arm vein for blood draws.

Lumbar puncture (LP): Participants will have LPs performed during the Baseline Visit and Outcome Visit at 8 weeks, to provide CSF for measurement of biomarkers. Up to a total of 15 mL of CSF will be collected on each of those two visits. CBC, PT, and PTT results should be available prior to each LP taking place. Participants will be encouraged to be well hydrated on the day of the LP.

In individuals in whom a landmark-guided LP at the bedside is deemed technically difficult by the medical staff (such as in the presence of degenerative lumbar spine disease, prior lumbar spine surgery, kyphosis/scoliosis or other conditions) or fails, a licensed Interventional Radiologist may perform the procedure under ultrasound or X-ray guidance (fluoroscopy-guided LP).

Cognitive testing: Logical Memory and CVLT will be administered using standard procedures. The MMSE will be administered only during the Screening Visit. In addition, we will administer EXAMINER, a software program (<http://examiner.ucsf.edu/index.htm>) implementing a battery of neuropsychological tests that reliably and validly assesses domains of executive function. This software was kindly given via a technology transfer request from [name] at the University of California – San Francisco. We will assess working memory, inhibition, set shifting, fluency, planning, insight, and social cognition and behavior. Neuropsychological testing will take approximately 1 hour to complete.

Brain MRI: In total, structural MRI, fMRI and MRS will last about 2 hours.

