Plasma ketones are strongly affected by alternate day CR acutely but not chronically;³⁹ our main objective for measuring them is to assess compliance with 5-2 CR.

We do not anticipate a change in physical activity in 5-2 CR versus “healthy living” control groups, because no change has been noted in our previous studies. Nonetheless, this is a common analysis requested by reviewers, to make sure that exercise effects did not contaminate diet effects.

The data from the gene array and DNA methylation array will be analyzed using residuals after adjustment for white blood cell differential count in linear regression models. We will take two approaches to analyze the data. First we will focus on candidate genes approach where we select specific expression probe or CpG sites; DNA for these studies will be collected during Baseline, Compliance and Outcome Visits. Second, we will run genome-wide association analysis for differences in cross sectional and longitudinal changes in gene expression or DNA methylation between the control and 5-2 CR group at each gene array probe or CpG site. DNA for genome-wide association analyses will only be collected during Baseline and Outcome Visits. For the cross sectional analyses, we will use a paired t-test at each visit, and mixed models for longitudinal analysis. In addition, we will look at overall patterns of gene expression and methylation using principle components, DIANE and hierarchical clustering tools to determine whether there are specific gene expression and methylation signature in association with 5-2 CR. As secondary analyses, we will also determine whether gene expression and DNA methylation patterns can predict the changes in metabolic, cognitive and neurochemical variables collected in this study. Within the 5-2 CR group, we will test the association between baseline levels of gene expression or DNA methylations at each probe/CpG site with longitudinal changes in the main outcome variables using mixed models.

10. b. Power analysis

The accrual number request is 100 participants. Our target sample size for completing the study is $N = 40$. There will be 20 participants in each group. We anticipate up to 60 participants will not meet inclusion criteria during the screening visit or may withdraw from the study. Enrollment will continue and withdrawals will be replaced until we have acquired complete data from 40 participants.

For power calculations, we used G*Power (<http://www.gpower.hhu.de/en.html>).

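### Compliance Visit samples follow an 8-hour fast of unclear scope while Baseline and Outcome samples follow 12 hours, so fasting length is confounded with visit in the five-visit candidate-gene and candidate-CpG series

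*Combined protocol and SAP*

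**What the plan says.** **Baseline (4.d.2).** "Participants will arrive on the NIA-Clinical Research Unit after a 12-hour fast".

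**Outcome (4.d.5).** "This visit will occur after a 12-hour fast, to ensure comparability of the mixed meal test with the Baseline Visit". This is the only reason the protocol gives for matching fasts, and it concerns the meal test alone. Section 4.d.6 adds, for the meal test at both visits: "A blood draw will take place before subjects consuming the liquid meal". The biomarker sample at Baseline and Outcome is therefore taken after the 12-hour fast.

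**Weeks 2, 4 and 6 (4.d.4).** "These visits will take place during the second of the two consecutive restriction days for the 5-2 CR group", or on any day for the healthy-living "diet group after an 8 hour fast". The 5-2 CR clause states no fast of its own. Table 1 marks "Fasting Blood Draw" at these visits without splitting by arm and without a duration.

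**What the samples feed (10.a).** For the candidate-gene approach: "DNA for these studies will be collected during Baseline, Compliance and Outcome Visits". For the other approach: "DNA for genome-wide association analyses will only be collected during Baseline and Outcome Visits". The only adjustment planned for the array data is for white-cell differential count. Table 2 lists β-hydroxybutyrate at the same five visits, and also lists plasma for exosomes, cytokines and AD biomarkers at the Compliance Visits.

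**The concern.** Three of the five time points in the candidate expression and candidate-CpG series are sampled under a different fasting rule from the first and last. Any marker that moves between 8 and 12 hours without food would step at Week 2 and step back at Week 8, with no diet effect needed. Fasting length is fixed by visit type, time since last intake is not recorded, and no model term covers it, so the two cannot be separated once the blood is drawn. Change from baseline within groups is a declared comparison (Section 1, study aims and overview), and that kind of comparison takes the shift in full.

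The wording adds a second problem. If the 8 hours bind controls only, the fast in the 5-2 CR arm is unspecified at Weeks 2, 4 and 6. That is the arm in which ketones serve as the objective compliance check. Section 4.a.2 reads them against absolute ranges (2–2.5 versus 0.5–1.0 μM/mL) that carry no fasting duration.

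**Working it through.** **Step 1. Fasting hours by visit, from 4.d.2, 4.d.4 and 4.d.5.**

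| Reading of 4.d.4 | Arm | Baseline | Wk 2 | Wk 4 | Wk 6 | Outcome |
|---|---|---|---|---|---|---|
| Both arms | each | 12 | 8 | 8 | 8 | 12 |
| Controls only | control | 12 | 8 | 8 | 8 | 12 |
| Controls only | 5-2 CR | 12 | not stated | not stated | not stated | 12 |

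**Step 2. Where a shift would go.** Let d be the effect on a marker of an 8-hour rather than a 12-hour fast.

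- Within arm, Baseline to Week 2, 4 or 6: the change carries +d.
- Between arms, same contrast, both-arm reading: d − d = 0 if the effect is equal in the two arms.
- Between arms, controls-only reading: d_CR − d, where d_CR is undefined because no fast is stated for 5-2 CR.
- Baseline to Outcome, either reading: 0, because both follow 12 hours.
- Among Weeks 2, 4 and 6: 0, provided each arm keeps one fast across those visits.

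**Step 3. Which planned analyses are touched.** Section 10.a defines Time as Baseline versus Outcome for the primary and each secondary scalar measure, so those models carry 0. The genome-wide arrays use the same two visits and also carry 0. Only series that include Compliance Visits are exposed: candidate expression, candidate CpG sites, the reading of ketones, and any later longitudinal use of the Compliance Visit plasma.

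**Step 4. Illustration of size.** The documents give no value or sign for d. Assume 20 per arm, correlation 0.4 (Section 10.b, assumed there for the IRS-1 ratio and borrowed here), one-tailed alpha 0.05, and no true diet effect.

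- Standard error of a within-arm change = sqrt(2 × (1 − 0.4)/20) = 0.245 SD; noncentral t, 19 df.
- Standard error of a between-arm difference in change = sqrt(2) × 0.245 = 0.346 SD; noncentral t, 38 df.

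| Contrast | Shift (SD) | Rejection rate if shift favours the hypothesis | If it opposes it |
|---|---|---|---|
| Within arm | 0.2 | 19.6% | 0.7% |
| Within arm | 0.3 | 32.1% | 0.2% |
| Between arms (difference in shift) | 0.1 | 8.7% | 2.7% |
| Between arms (difference in shift) | 0.3 | 21.4% | 0.6% |

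The nominal rate is 5% throughout. A favourable within-arm shift of 0.5 SD would give 62.7%. These rates apply to a Baseline-to-Week-2 test, which the plan does not name.

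**The case against.** The strongest reply is that no specified test is affected. Section 10.a says candidate samples are collected at Compliance Visits but names no visit-level contrast for them, and the scalar models use two visits with the same fast. That stands. The exposure arises when the five-visit candidate series is analysed as a time course, which is the evident reason for collecting it, but the plan sets out no such test.

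A reader might infer that between-arm comparisons are biased because controls fast after ordinary eating and 5-2 CR participants after a restricted-day shake. The documents do not support this. That difference is the treatment contrast, 5-2 CR visits are deliberately placed on the second restriction day, and it would remain at any matched fasting length.

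A reader might also infer that fed and fasted samples are mixed. Table 1 marks every draw as fasting and favours the both-arm reading, so on that reading only the duration differs. Table 1 gives no hours, however, and so does not settle what 5-2 CR participants are told.

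On ketones, the reply is that they are mainly a compliance check with no five-visit model, and that Compliance Visits are comparable with one another. That is fair if the 8 hours cover both arms. If they cover controls only, the fast is unstated in the arm being checked.

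Finally, the error rates rest on assumed shifts and a borrowed correlation, and a one-tailed test loses rejections when the shift runs the other way. Both directions are shown above for that reason.

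**Conclusion.** The point holds as a minor design weakness confined to exploratory series. As written, fasting duration is fully confounded with visit type in any within-arm change from Baseline to Week 2, 4 or 6 for candidate genes and candidate CpG sites, and the fast behind the 5-2 CR ketone readings is not clearly stated. Between-arm contrasts at those visits are affected only if the fast, or its effect, differs by arm.

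It would be wrong to conclude that the primary outcome, the main mixed models or the methylation results as a whole are compromised. The first two use 12-hour samples only, and so does the genome-wide methylation outcome listed in 9.b. The size and direction of any shift are unknown, so the percentages show how sensitive such a contrast would be and do not estimate an error rate for this trial.

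**What to change.** Reconcile 4.d.4 with 4.d.2 and 4.d.5 so that one stated fasting length applies to both arms at every visit feeding the same longitudinal series. Add a field for time since last intake at each draw. Which length to adopt is for the investigators.

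If the lengths are not matched, say in 10.a that within-arm changes from Baseline to Weeks 2–6 will not be interpreted as diet effects. Rely instead on Baseline–Outcome changes and on comparisons among the Compliance Visits, with the fast held constant across them.

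The visit day needs reconciling at the same time: 4.d.1 puts the 5-2 CR Outcome Visit on the second restriction day and 4.d.5 on the first, so matching the fast alone would not make Outcome comparable with the Compliance Visits.

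Cost: one sentence and one form field. If the longer length is used, participants fast somewhat longer before three one-hour visits. Under the fallback, all three Compliance time points drop out of change-from-Baseline contrasts.
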